6. SERIOUS ADVERSE EVENTS REPORTING

A Serious Adverse Event (SAE) is any untoward medical occurrence that results in at least one of the following outcomes:

- Results in death
- Is life-threatening
- Requires inpatient hospitalization or prolongation of existing hospitalization
- A persistent or significant incapacity or substantial disruption of the ability to conduct normal life functions
- Is a congenital anomaly/birth defect
- Requires medical or surgical intervention to prevent permanent impairment or damage

SAE collection will coincide with the subject providing informed consent to participate in the study and will conclude 30 days after a subject's last dose of study medication. Should a serious and/or unexpected adverse event occur, the Investigator must notify Braintree Laboratories immediately. The Investigator will make a decision regarding continuing the subject's study participation, and may request input from Braintree Laboratories. The Investigator will be responsible for recommending or providing the subject with appropriate medical therapy. All subjects experiencing serious adverse events will be followed until satisfactory resolution occurs. Braintree Laboratories must be kept apprised of all follow-ups relative to serious adverse events. In addition, Investigators must comply with the SAE reporting requirements of the Institutional Review Board with oversight of the study.

Any serious and/or unexpected adverse events that occur during the study will be reported to Braintree Laboratories as follows:

Contact Telephone Numbers:

During Business hours (M-F, 8:30 am – 5:00 pm EDT)	[contact]
After hours or weekends	[contact]

Braintree Laboratories and its medical monitor will review the report and determine whether an FDA Form 3500A will also be completed and sent to FDA.

7. INSTITUTIONAL REVIEW BOARD AND INFORMED CONSENT

Institutional Review Board (IRB) review and approval of the study protocol and Informed Consent Form will be obtained prior to initiation of the study. Amendments to the study protocol and consent form generated during the course of the study will also require IRB approval.

8. MANAGEMENT OF INTERCURRENT EVENTS

8.1. Modification of Protocol

Neither an Investigator nor Braintree Laboratories will modify the protocol without first obtaining the concurrence of the other and the IRB. Investigators that continually violate the protocol or commit a serious violation may be subject to termination from the study. The study may be halted if at any time an Investigator or Braintree Laboratories deems the incidence or severity of adverse events to be unacceptable.

8.2. Subjects Discontinued from the Study

Subjects may be dropped from the study for any of the following reasons:

- 1) Subject took prohibited medications during the Treatment Period
- 2) An adverse event requiring discontinuation (including failure to tolerate study medication).
- 3) The Investigator decides that the subject should be dropped from the study (e.g. serious adverse event, protocol violation, non-compliance).
- 4) The subject decides to withdraw from the study. Subjects are free to withdraw their consent and discontinue participation in the study at any time.

Braintree Laboratories should be contacted if possible prior to discontinuation of any subject. If a subject is discontinued from the study, Braintree Laboratories must be notified with an explanation for all discontinuances.

9. DATA ANALYSIS

9.1. Sample Size

Consistent with *ICH E1A Guideline for Industry, the Extent of Population Exposure to Assess Clinical Safety: for Drugs Intended for Long-term Treatment of Non-Life-Threatening Conditions (March 1995)*, 300 subjects will be treated with BLI400 for 12 months. This will allow for detection of adverse events that may increase in frequency or severity over time.

9.2. Parameters to be Analyzed

The primary objective of this study is to investigate the safety of BLI400 used chronically for 12 months in subjects with constipation. Safety will be analyzed using ECG, vital signs, chemistry, hematology and urinalysis and adverse event data. Treatment emergent adverse event rates will be descriptively presented by preferred term, severity, and relationship to treatment.

9.3. Planned Analyses

9.3.1. Demographic and Baseline Characteristics

Baseline demographic characteristics will be tabulated with N, mean, standard deviation, and range of values where appropriate

- Age
- Gender
- Race/ethnicity
- Constipation History

9.3.2. Safety Analyses

Analysis of safety will be performed using the modified Intent to Treat population (see [Section 9.4](#)).

Adverse Events

Adverse Events will be coded using the MedDRA classification to provide a preferred term and primary system organ class for each event. Proportions of subjects with adverse events will be presented for the overall study population, and each demographic subgroup (age, gender and race). Tables of AEs will be presented by system organ class and preferred term, and include overall totals for AEs within each system organ class. Counting will be done by subject and not by event. A table of counts and percentages will also be made of those subjects with SAEs or AEs which led to withdrawal from the study.

Treatment-emergent AEs are defined as adverse events that had an onset day and time on or after the day and time of the first dose of study drug until the Day 374 Follow-up Call. Adverse Events having missing onset dates will be considered as treatment emergent.

The difference in adverse event rates between study periods will be tested by Chi-Square or Fisher's exact test with 95% confidence intervals.

Laboratory Parameters

Summary statistics (i.e., mean, minimum, maximum, standard deviation, and number of subjects) will be presented for each laboratory parameter at each visit. Laboratory data will be summarized for the overall population and the elderly and non-elderly subgroups. When calculating the summary statistics only, the last observation within a visit window will be used if there are multiple observations. Changes from baseline (Visit 1) will be presented in a similar format. An additional listing will be provided of those subjects who have clinically significant laboratory values. The data will also be presented as shift tables and clinically significant abnormalities will be examined.

Results of laboratory tests for the change from baseline (Visit 1) and group differences will be tested using ANOVA.

Vital Signs

Summary statistics (i.e., mean, minimum, maximum, standard deviation, and number of subjects) will be presented for each vital sign at each visit and compared to the values obtained at Visit 1. When calculating the summary statistics only, the last observation within a visit window will be used if there are multiple observations. The data will also be presented as shift tables and clinically significant abnormalities will be examined.

ECG variables will be tabulated and presented for data collected at each visit. Data will be tabulated and summarized with descriptive statistics (N, mean, SD, CV%, SEM, minimum, and maximum) for each of the ECG variables. The differences in ECG variables between Visit 1 (Baseline), Visit 2 and Visit 6 will be tested using ANOVA.

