3.2. Number of Subjects

Approximately 300 constipated subjects will be enrolled into this study, including approximately 100 elderly subjects (≥ 65 years of age at Visit 1).

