5. ADVERSE EVENTS

5.1. Adverse Event Definition and Reporting

An Adverse Event (AE) is any untoward medical occurrence associated with the use of a drug in humans, whether or not considered drug related. An AE can therefore be any unfavorable and unintended sign (including a clinically significant abnormal laboratory finding), symptom, or disease temporally associated with the use of a medicinal (investigational) product.

Adverse event collection will coincide with the subject providing informed consent to participate in the study and will conclude with the end of study participation at Day 374 Follow-up Call. Diarrhea should be reported as an adverse event if a subject has more than 3 watery stools per day. Subjects with clinically significant laboratory results at Visit 6 which are classified by the Investigator as adverse events should return for a repeat blood draw. Subjects will be instructed to report promptly adverse events to the Investigator. The Investigator will record date/time of report, date/time of onset, description of the adverse event, severity of adverse event, action(s) taken regarding treatment of the event, action(s) taken regarding study participation, duration of adverse event, and the Investigator's assessment of relationship of adverse event to study treatment.

The Investigator should assess the severity of each adverse event using the following categories:

Grade	Severity	Description
1	Mild	Barely noticeable, does not influence functioning Causing no limitations of usual activities
2	Moderate	Makes participant uncomfortable, influences functioning Causing some limitations of usual activities
3	Severe	Severe discomfort, treatment needed Severe and undesirable, causing inability to carry out usual activities
4	Life threatening	Immediate risk of death Life threatening or disabling
5	Fatal	Causes death of the participant

Braintree Laboratories, Inc.
Protocol Number BLI400-303

Confidential

The Investigator should assess the relationship to study drug for each adverse event using the following categories:

Categories of Attribution:	Description
UNRELATED	There is no evidence of any causal relationship.
POSSIBLE	There is some evidence to suggest a causal relationship (e.g., the event occurred within a reasonable time after administration of the trial medication). However, the influence of other factors may have contributed to the event (e.g., the patient's clinical condition, other concomitant events).

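### Section 9.1 promises detection of adverse events that grow in frequency or severity over time, but no planned AE output shows severity over time, and by-subject counting largely masks repeat episodes

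*Combined protocol and SAP*

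**What the plan says.** The analysis plan is Section 9 of the protocol.

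- **Purpose (9.1).** The size is stated as "300 subjects will be treated with BLI400 for 12 months", citing an ICH guideline on extent of exposure, and then: "This will allow for detection of adverse events that may increase in frequency or severity over time".
- **Severity (9.2).** "Treatment emergent adverse event rates will be descriptively presented by preferred term, severity, and relationship to treatment". No visit, month or period appears.
- **Counting (9.3.2).** After describing the tables by system organ class and preferred term, the plan adds: "Counting will be done by subject and not by event".
- **Time (9.3.2).** There is one time-based AE analysis: "The difference in adverse event rates between study periods will be tested by Chi-Square or Fisher's exact test with 95% confidence intervals". The periods are not defined, and Section 3.3 names only a single 12-month Treatment Period.
- **Other AE output (9.3.2).** Subjects with serious AEs or AEs leading to withdrawal are tabulated, with no time split stated. Treatment emergence is defined by onset alone.
- **Recording (5.1).** Onset date and time, duration and severity are recorded for each AE. The instruction on grading is: "The Investigator should assess the severity of each adverse event using the following categories". Nothing says what to do when the grade of an ongoing AE changes or when an AE recurs.

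**The concern.** Safety is the only study objective, and Section 9.1 gives detection of change over time as what 300 subjects for a year will provide. Such a change can take three forms: more subjects affected, more episodes in the same subjects, or higher grades. The planned AE outputs are suited to the first form only.

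The other two matter for this product. Section 5.1 describes the expected reactions as gastrointestinal, transient and quick to subside when the dose is adjusted or stopped. Events of that kind can recur in the same people, so a loss of tolerability may appear as repetition or worsening in subjects already counted. If the outputs do not display these patterns, a flat incidence table could be read as stable tolerability. A grade change that was not dated when it happened may also be unrecoverable afterwards.

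**Working it through.** **The plan's own figure.** The 300 cannot be reproduced by formula: no AE rate, size of rise, alpha or power is given. As a plausibility check, the chance of seeing at least one AE with a true 1% rate is 1 − 0.99^300 = 95.1%, or 1 − 0.99^210 = 87.9% if only 210 are exposed (assumed 30% loss). This concerns seeing an event at all, not seeing a rise. No stated figure is contradicted.

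**Inputs.** From the documents: 300 subjects, by-subject counting, and a chi-square or Fisher's exact test between periods. Assumed: two equal periods, 300 subjects in each, two-sided alpha 0.05, each subject counted at most once per period, and every rate below. Periods are treated as independent samples, as the planned test treats them, although the same subjects contribute to both.

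Power for two proportions is Φ[(|p2 − p1| − 1.96·se0)/se1], with se0 from the pooled proportion and se1 from the separate ones. It counts rejections in the direction of the rise only, so it can fall slightly below 5% for very small differences.

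**1. More subjects affected.** A rise from 10% to 20% of subjects gives 93% power (88% if the later period has 210). A rise from 5% to 10% gives 64% (58%). The planned test can see this form.

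**2. More episodes in the same subjects.** Let a fraction f be susceptible, with Poisson mean m episodes per period. The share of subjects with at least one episode is f(1 − e^−m).

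Worked case, f = 0.20, m from 2 to 6:
- Events: 300 × 0.20 × 2 = 120, and 300 × 0.20 × 6 = 360.
- By subject: 0.20 × (1 − e^−2) = 17.3%, and 0.20 × (1 − e^−6) = 19.95%.
- Power by subject: (0.0266 − 1.96 × 0.0318)/0.0318 ≈ −1.12, so Φ ≈ 13%.
- Power on mean episodes per subject: the variance is f(m + m²) − (fm)², that is 1.04 and 6.96. The standard error is √(8.00/300) = 0.163. Then 0.80/0.163 − 1.96 = 2.94, so Φ is over 99%.

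| f | m, early to late | Events | Subjects with AE | Power by subject | Power by event |
|---|---|---|---|---|---|
| 10% | 1 to 3 | 30 to 90 | 6.3% to 9.5% | 30% | 86% |
| 10% | 2 to 6 | 60 to 180 | 8.7% to 10.0% | 8% | 91% |
| 10% | 3 to 9 | 90 to 270 | 9.5% to 10.0% | 4% | 93% |
| 20% | 1 to 3 | 60 to 180 | 12.6% to 19.0% | 57% | 99% |
| 20% | 2 to 6 | 120 to 360 | 17.3% to 19.95% | 13% | >99% |
| 20% | 3 to 9 | 180 to 540 | 19.0% to 20.0% | 5% | >99% |
| 30% | 1 to 3 | 90 to 270 | 19.0% to 28.5% | 79% | >99% |
| 30% | 2 to 6 | 180 to 540 | 25.9% to 29.9% | 19% | >99% |
| 30% | 3 to 9 | 270 to 810 | 28.5% to 30.0% | 6% | >99% |

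Events triple in every row, while by-subject power runs from 4% to 79%.

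**3. Higher grade, same incidence.** Hold the any-AE rate at 20% in both periods and let the severe share rise from 5% to 20%. Severe AEs then affect 0.20 × 0.05 = 1% of subjects early (3 of 300) and 0.20 × 0.20 = 4% late (12 of 300). The planned any-AE comparison has nothing to respond to and rejects only at its 5% error rate. A by-grade comparison would have Φ[(0.030 − 1.96 × 0.01275)/0.01269] = about 65% power. With severe shares of 10% and 30% (2% to 6% of subjects) it would have 71%.

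**4. Recording.** The by-grade comparison needs a date for each worsening. Section 5.1 supplies onset and duration but no rule for a grade that changes, so a mild Month 1 AE that becomes severe in Month 8 has no assured date of worsening.

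**The case against.** By-subject counting is customary and stops a few subjects from dominating a rate. The sentence sits with the incidence tables, and nothing bars a listing or a supplementary event count. Section 9.3.2 also plans a between-period comparison, in which an early-affected subject could count again on recurrence. All this stands. A reader might infer that a rise in frequency cannot show at all, or shows only through newly affected subjects. The documents do not support either reading.

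A reader might also infer that late worsening is credited to the early period, so that tables would show severe AEs early and none late. That needs two rules the protocol does not contain: keep the maximum grade, and allocate it by onset. No severity-by-period table is planned that could be reversed in this way. The supportable point is that the table is absent and the recording rule unstated.

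Finally, Section 9.3.3 presents PAC-SYM at each visit by severity category, and laboratory values and vital signs have visit summaries and shift tables. This is partial cover. PAC-SYM includes abdominal discomfort, pain, bloating and cramps, but not diarrhea, nausea, vomiting or flatulence. The serious-AE and withdrawal table could carry an indirect severity signal, but it has no time split.

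**Conclusion.** The point holds in limited form. Followed as written, the plan yields no AE output showing severity over time, and its counting rule largely masks repeat episodes within a period. The stated purpose in Section 9.1 is therefore met only for a rise in the share of subjects affected, and only if periods are defined and subjects are counted once per period. If subjects were instead counted once over the whole study, the frequency gap would be wider.

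The severity gap follows from the text alone. The size of the frequency gap rests on the assumed scenarios: power of 4% to 79% by subject against 86% to 100% by event when episodes triple. This goes beyond missing detail, because a stated counting rule and a pooled severity presentation do not serve the plan's own purpose. It should be corrected, but it does not invalidate the safety analysis.

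**What to change.** **Section 9.3.2.** Keep the by-subject incidence tables. Define the study periods and the subjects at risk in each, and count each subject once per period for incidence. Then add, by period:

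1. the number of episodes, or an exposure-adjusted event rate;
2. subjects with an AE that started or worsened in the period, by maximum grade in that period.

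**Section 5.1.** Record any change in the grade of an ongoing AE with its date, linked to the original AE. The link matters: a worsening entered as an unlinked new record would inflate the episode count in table 1.

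**Cost.** One eCRF completion rule and two or three extra tables. Onset and duration are already collected, and no visits or subjects are added. The recording rule has to be in place while data are being collected, whereas the tables can be specified later, before analysis.

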4.2. Treatment Period

4.2.1. Treatment Day 1

Starting on the morning of Treatment Day 1 (the day after Visit 1), subjects will measure 2 capfuls of study medication and ingest it mixed in a beverage of their choice. Subject will take a daily dose of 2 capfuls until they return for Visit 2. Subjects that develop persistent diarrhea or loose stools should contact their study center. These subjects will be allowed to adjust their dose down to 10.5g (1 capful) per day.

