PROBABLE	There is evidence to suggest a causal relationship, and the influence of other factors is unlikely .
DEFINITE	There is clear evidence to suggest a causal relationship, and other possible contributing factors can be ruled out .

In published Phase 3 studies, adverse events associated with BLI400 administered at doses required for effective treatment of constipation included flatulence, nausea, vomiting, abdominal cramping or pain and bloating. These adverse reactions were transient and subsided rapidly upon dose adjustment or cessation.

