APPENDIX B

Patient Assessment of Constipation – Symptom (PAC-SYM) Questionnaire

Patient Assessment of Constipation-Symptom Questionnaire (PAC-SYM)

This questionnaire asks you about your constipation symptoms in the past two weeks. Answer each question according to your symptoms, as accurately as possible.

Please indicate how severe your symptoms have been during the past two weeks. If you have not had the symptom during the past two weeks, check 0. If the symptom seemed mild, check 1. If the symptom seemed moderate, check 2. If the symptom seemed severe, check 3. If the symptom seemed very severe, check 4. Please be sure to answer every question.

How severe have each of these symptoms been in the last two weeks?	Absent 0	Mild 1	Moderate 2	Severe 3	Very Severe 4
1. discomfort in your abdomen					
2. pain in your abdomen					
3. bloating in your abdomen					
4. stomach cramps					
5. painful bowel movements					
6. rectal burning during or after a bowel movement					
7. rectal bleeding or tearing during or after a bowel movement					
8. incomplete bowel movement, like you didn't "finish"					
9. bowel movements that were too hard					
10. bowel movements that were too small					
11. straining or squeezing to try to pass bowel movements					
12. feeling like you had to pass a bowel movement but you couldn't (false alarm)					

Proprietary information of Janssen Research Foundation
 All rights reserved. 1997.

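### The treatment-emergent definition has no worsening clause: an adverse event that starts before the first dose and becomes more severe on BLI400 drops out, and worsening of a long-standing symptom is counted or not depending on the site

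*Combined protocol and SAP*

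**What the plan says.** Section 9.3.2 (Adverse Events) gives the rule: "Treatment-emergent AEs are defined as adverse events that had an onset day and time on or after the day and time" of the first dose, with the window closing at the Day 374 call. One supplement follows: "Adverse Events having missing onset dates will be considered as treatment emergent". Section 9.2 makes the resulting rates a named output for the primary safety objective: "Treatment emergent adverse event rates will be descriptively presented by preferred term, severity, and relationship to treatment".

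Section 5.1 defines an adverse event broadly: "An AE can therefore be any unfavorable and unintended sign (including a clinically significant abnormal laboratory finding), symptom, or disease temporally associated" with use of the product. It does not say whether a pre-existing symptom that gets worse is a new event, or what onset date it should carry. On timing, the same section states that "Adverse event collection will coincide with the subject providing informed consent to participate in the study", and section 4.2.1 places the first dose later: "Starting on the morning of Treatment Day 1 (the day after Visit 1), subjects will measure 2 capfuls of study medication".

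On the expected effects, section 5.1 reports that adverse events in published Phase 3 studies "included flatulence, nausea, vomiting, abdominal cramping or pain and bloating". The PAC-SYM in Appendix B, completed at Visit 1 before any dosing, treats several of the same complaints as part of the disease: "This questionnaire asks you about your constipation symptoms in the past two weeks". Its items 1 to 4 are abdominal discomfort, abdominal pain, bloating and stomach cramps.

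**The concern.** A treatment-emergent definition normally has two limbs: events that are new after the first dose, and events already present that get worse after it. This plan has only the first.

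The second limb matters more than usual here, because some of the effects expected of the drug are also symptoms of the condition being treated. A subject with mild bloating at entry who develops severe bloating on lactitol has had the kind of event this study exists to find. Safety is the primary objective, and there is a single open-label arm, so no control group carries the same undercount to offset it. The plan is also uneven on this point. Laboratory values and vital signs get shift tables that show worsening from baseline, and missing onset dates are resolved towards inclusion, whereas adverse events that worsen have no provision.

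**Working it through.** The plan states no figure on this point, so there is nothing to reproduce. The check is to apply the rule as written to the situations that can arise.

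**Pre-dose interval.** Consent is at Visit 1 (Day 0) and dosing starts the next morning, so the interval is about 1 day. Under section 4.1, subjects ineligible because of prohibited medication may be washed out for 14 days. The Visit 1 procedures are then repeated, but consent is not. Their interval is at least 14 days.

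**Applying the 9.3.2 rule.**

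| Situation | Recorded onset | Treatment-emergent? |
|---|---|---|
| A. New symptom after first dose | After first dose | Yes |
| B. Event begins between consent and first dose, then becomes more severe on drug | Before first dose | No |
| C. Medical-history symptom worsens; site opens an event dated at the worsening | After first dose | Yes |
| D. Medical-history symptom worsens; site dates it to when the symptom began, or records no event | Before first dose, or none | No |
| E. Onset date missing | Missing | Yes |

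B follows from the wording. C and D are the same clinical occurrence with different answers, and section 5.1 neither requires nor forbids either way of recording it.

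**Overlap with expected effects.** Section 5.1 lists flatulence, nausea, vomiting, abdominal cramping or pain, and bloating. PAC-SYM items 1 to 4 match the last two entries. Flatulence, nausea and vomiting are not PAC-SYM items. The overlap is real but partial.

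**Size.** For B, the pool is the subjects with an event dated in the pre-dose interval that later worsens. The documents give no basis for a count.

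For the C/D ambiguity, only an upper-end illustration is possible. Let N = 300 (section 9.1), b = share of subjects with the symptom at entry, and r = probability of a new or worsened event, taken as equal with and without the symptom. Both b and r are assumptions. If every site handled every worsening as in D:

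- counted = N(1 − b)r
- omitted = N × b × r
- total with worsening included = N × r
- relative undercount = (N × b × r)/(N × r) = b

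| b | r | Counted | Omitted | Total |
|---|---|---|---|---|
| 20% | 5% | 300 × 0.8 × 0.05 = 12 (4%) | 300 × 0.2 × 0.05 = 3 | 15 (5%) |
| 40% | 10% | 300 × 0.6 × 0.10 = 18 (6%) | 300 × 0.4 × 0.10 = 12 | 30 (10%) |
| 60% | 20% | 300 × 0.4 × 0.20 = 24 (8%) | 300 × 0.6 × 0.20 = 36 | 60 (20%) |

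These counts are per symptom and assume that no site records worsening separately. A spread from 3 to 36 shows that the assumptions decide the answer.

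**The case against.** The strongest reply is that the rule turns on the onset of an adverse event, not of a symptom. Section 5.1 ties an adverse event to use of the drug. A complaint present for years is then naturally medical history, which is collected at Visit 1. The untoward occurrence is the worsening, its onset is after the first dose, and it counts. This is a fair reading, and it defeats the inference, which a reader might draw, that every worsening of a baseline symptom is excluded. It does not make that reading the rule: the protocol does not state it, and a multi-center study leaves each site to decide. Nor does it rescue events already recorded between consent and first dose.

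A reader might also infer that a large share of the 300 subjects is affected. The documents do not support that. Pain and bloating are not entry requirements (section 3.5.1), Rome II irritable bowel syndrome and frequent loose stools are excluded (section 3.5.2), and every PAC-SYM item can be answered as absent. The interval in which an event can be recorded before dosing is about a day for most subjects. Counting is by subject, so someone with worsened bloating and a separate new gastrointestinal event is already in the system organ class total.

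Finally, such worsening would not be invisible. The table of serious events and withdrawals, and the tables by system organ class and preferred term, are not expressly limited to treatment-emergent events. PAC-SYM change from baseline is reported at each visit. That stands, but PAC-SYM is analysed as efficacy, covers only the preceding two weeks at visits two to three months apart, and does not feed the adverse event tables. Non-serious worsening without withdrawal can still be absent from the rates that section 9.2 names.

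**Conclusion.** The point holds in a limited form. As written, an adverse event with a recorded onset between consent and first dose that becomes more severe on BLI400 is not treatment-emergent. For a symptom held as medical history, the plan is ambiguous rather than exclusionary, and handling may differ by site.

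The direction is certain: omitting worsened events can only lower the treatment-emergent rate. The size is not known. It would need the frequency of pre-dose events, the baseline prevalence of abdominal symptoms, the rate of worsening and the sites' recording habits, and the documents give none of these. The tabulated counts are an upper-end illustration for the ambiguous group alone and should not be quoted as an estimate of bias.

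This is worth correcting because it affects a named output of the primary objective and costs little to change. It does not undermine the study.

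**What to change.** Two sentences, which belong together.

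- **Section 9.3.2:** define a treatment-emergent adverse event as one with onset on or after the first dose, or one present before the first dose that increased in severity or became serious on or after it. Keep the end of the window and the missing-date rule as they are.
- **Section 5.1:** state that worsening of a pre-existing symptom or condition beyond its pre-dose level, including one held as medical history, is recorded as a new adverse event with its own onset date.

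The 5.1 sentence has to be in force while data are collected. Section 5.1 asks for a severity for each event but does not ask for severity before and after dosing, so worsening that was never recorded cannot be reliably recovered at analysis.

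No new visits or procedures are needed, only the amendment and guidance to sites. The downside is a slightly higher treatment-emergent rate that will include some natural fluctuation of constipation symptoms, which a single-arm study cannot separate from drug effect. Flagging events that qualify through worsening, so that the tables can be read with and without them, would keep that visible.
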